Outcome measure:

	Outcome Name	Measuring Tool	Measuring Unit
Primary Outcome	Duration of space closure	Dental digital Model Records of visits	
- Scanned digital models in (mm)
o Models taken every montho Analysed using 3 Shape Software- computerized record system of the recruited patient (months, days, years)

Secondary Outcomes	Anchorage loss	Digital models	- Linear measurement in mm
	Pain	Pain scoring sheets given to patients	- VAS scoring from 1-10 ^(Fig 1)

B-Research question:

Will en-masse retraction offer shorter treatment duration compared to two steps retraction, in patients having maxillary protrusion?

Objectives of the study

Research hypothesis:

The null hypothesis (H_0) of this research is that there's no difference between both en-masse and two steps techniques on duration of retraction during en-masse and two steps retraction following 1st premolar extraction.

Primary objective:

Evaluating the duration of En-masse and two steps retraction using friction mechanics.

Secondary objectives:

Assessing the amount of anchorage loss, pain and discomfort during retraction. In addition to this, of anterior teeth will be measured following en-masse and two steps retraction using friction mechanics.

Study design:

This is a randomized clinical trial with two arms parallel group, and 1:1 allocation ratio. In one group, will receive frictional mechanics during En masse retraction, while the other group will receive frictional mechanics during two steps retraction. The duration of retraction will then be compared between both interventions.

Material and Methods

I) Participants, Interventions, and Outcomes

A] Study Setting:

The study will be performed in the clinic of the Orthodontic Department at the Faculty of Oral and Dental Medicine, Future University in Egypt. The recruited sample would be from the Egyptian urban and rural population.

B] Eligibility criteria:

Inclusion criteria: for the participants include the following:

1. Age range (14-24)
2. Adolescent & Adult patients (both genders)
3. Patients with maxillary protrusion requiring first premolars extraction (Bimaxillary Protrusion or Class II division 1 cases) as confirmed from lateral cephalometric, pre-treatment records & from clinical examination.
4. Patients with fully erupted permanent teeth (not necessarily including the third molar).
5. Cases requiring maximum anchorage during retraction.

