6. Minimal crowding 2-3 mm.

Exclusion Criteria: for the involved subjects included:

1. Patients suffering from any systemic diseases interfering with tooth movement.
2. Patients with extracted or missing permanent teeth. (Except for third molars).
3. Patients with badly decayed teeth.
4. Patients with any parafunctional habits (i.e. Bruxism, tongue thrusting, mouth breathing, etc...).
5. Patients with previous orthodontic treatment.

C] Interventions:

➤ Medical History Questionnaire:

For every patient, to exclude the presence of any systemic condition interfering with orthodontic treatment.

➤ Clinical Examination:

Oral structures will be examined to identify caries, fracture or missing teeth. Gingival tissues will be carefully examined for any gingivitis, periodontitis, recession, or lesions.

➤ Diagnosis

Check the potential patient to fulfill the previously mentioned inclusion criteria. Every participant will be asked to sign an informed consent about the study. Full set of records (study models, panorama radiograph and lateral cephalometric radiographs, photos) will be taken for every patient as part of the routine procedure for treatment of patients in the clinic of the Orthodontic Department, Future University in Egypt.

➤ Clinical Procedure:

After taking pre-treatment records, every patient will receive:

- Miniscrews will then be placed in the upper arch between the second premolar and first molar.
- The patient will be referred for extraction of first premolars.

- Anchorage will be secured, followed by Leveling and alignment for the bonded and banded teeth through following the wire sequence: 0.014 NiTi, 0.016×0.022 NiTi and 0.017×0.025 StSt.
- Bonding of all teeth except for first premolars and banding/bonding the first and second molars will be done using Roth prescription brackets (0.022 x 0.028 slot)*.
- After leveling and aligning is completed (right before retraction), the patient will be referred for the uptake of pre-intervention records for en masse group (Impression for models, photos extra oral and intra oral and pain questionnaire).
- For two step group canine retraction will take place on a 0.017×0.025 StSt arch wire, once canine retraction stage is completed, the patient will be referred for the uptake of pre-intervention records.

➤ **Acquisition of pre-intervention records:**

- Alginate impressions will be taken before retraction (without the arch wire in place) followed by digital scanning of produced models.

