- Photos (Extra and intra oral).
- Pain questionnaire distributed with explanatory session on it.

➤ **Begin of Retraction:**

- Crimpable hooks added to the arch wire (0.017"x0.025" Stainless steel) distal to the lateral incisor passing near the center of resistance of the anterior segment.
- A ligature wire extending between the second premolar and miniscrews will be used for proper anchorage control.

- Retraction will start on a 0.017"x0.025" Stainless steel wire using elastomeric chain (force applied will be 200 g per side) (24) extending between the crimpable hooks and the molar hooks.
- The force will be measured by a force gauge and reactivated every 4 weeks maintaining constant force of retraction all over the retraction phase.

➤ **Follow up visits**

Patients will be asked to attend for follow up sessions every 4 weeks for:

- Evaluation of miniscrews stability.
- Replacement of the power chain to maintain a force of 200 gm per side for en masse group and 160 gm per side for two step group.
- Impression taking to assesses amount of space closure.
- Recording the pain scoring sheet.

➤ **Criteria for discontinuing or modifying the allocated intervention:**

In cases of prolonged swelling or pain related to the miniscrew, the patient will be given strict oral hygiene measures and may wait for three weeks before the beginning of retraction.

In cases of loose or broken miniscrews, the screw will be removed and replace the miniscrew after total resolution of the inflammation.

In case of non compliant patients.

□ **Post-retraction Questionnaire:**

The patients of both groups will be asked to fill in questionnaires regarding their experience with their allocated technique, during the whole retraction period from day of extraction till the end of retraction.

□ **Retraction records**

Following en-masse and two steps retraction, patients will be referred to the same radiology center to acquire the final cone-beam CT to assess the movement and inclination of anterior teeth.

The final dental model will be used to assess the rate of retraction and molar anchorage loss achieved throughout the study.

□ **Criteria of ending the retraction**

- Class I canine relation
- Normal overjet
- Balanced facial profile
- Closing extraction space

□ **Material Used**

- American Orthodontics Brackets, Roth prescription, 22 slot size.
- American Orthodontics Elastomeric power chains
- American Orthodontics Elastomeric O-ties
- American Orthodontics Ligature wire.

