- Miniscrew, 8 mm length x 1.6mm diameter TAD (Jeil).
- American Orthodontics Arch wires.
- American Orthodontics Molar bands/tubes.

D] Outcomes

[figure not shown]
Primary outcome: is to monitor the Duration of space closure during en-masse and two steps retraction. All outcomes will be assessed as the difference between T0 at the start of retraction and T1 after complete space closure.

Secondary outcomes: is to monitor the changes in the anterior teeth position (final anterior teeth tip, torque and vertical position), anchorage loss, presence of any root resorption and pain associated with the different methods used for retraction.

E] Participant timeline:

1. The principle investigator will screen the potential patients through careful clinical examination of patients at the orthodontic department, Faculty of Oral and Dental Medicine, Future University in Egypt.
2. All recruited patients should fulfil the previously mentioned inclusion and exclusion criteria.
3. Every participant will be asked to sign an informed consent before the beginning of the study.
4. After patient's enrolment, each participant will be asked for pre-intervention records to ensure proper diagnosis.
5. The principle investigator will randomly allocate the patients to one of the intervention groups.

6. Anchorage will be secured by placement of miniscrew, followed by extraction of the first premolar.
7. Active intervention will begin after proper levelling and alignment of the upper arch.
8. The principle investigator will take pre-retraction records for every participant T0.
9. Power chain is used for anterior segment retraction.
10. Each patient will come every 4 weeks for follow up visit, for appliance activation and uptake of impression for interim records + monitoring of recording the VAS sheet.
11. After complete space closure, the principle investigator will take post-retraction records for each participant T1.
12. Every patient will fill up a questionnaire regarding his experience during treatment.
13. The principle investigator will continue the normal treatment and achieve proper finishing for every patient after the end of the study.

F] Sample size calculation:

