Assignment to either intervention will occur before levelling and alignment stage.

D] Blinding:

Blinding of the operators: Blinding will not be possible for the operators during the application interventions and during the follow up visits. The principal operator is responsible for assigning subjects to interventions according to the concealed allocation, appliance activation at follow up visits, dental impressions and acquisition of dental casts.

Blinding of the outcome assessors: It is a single blinded study, therefore, only the outcome assessors will be blind. The patients name will be sealed from pre and

post radiographs and study models. Then two assessors will carry out, blindly and independently, the measurements and analysis of the study.

III) Data collection, management and analysis:

A] Data collection methods:

Primary outcomes:

1. Total Retraction Duration: to assess the timing of antero-posterior movement of anterior teeth and first molars, the principle investigator will take study models for every participant monthly during the follow up visits. Then will digitize the models and identify the landmarks, reference lines and planes on the pre, interim and post-retraction digital dental models for measurements reading. Also, by identifying the landmarks, reference lines and planes using CBCT taken before and after the completion of retraction.

Secondary outcome:

1. Anchorage loss: will be accessed by the principal investigator via CBCT taken before and after the completion of retraction by identifying the landmarks, reference lines and planes, then will interpret the measurements in degrees and millimeters.

2. Pain: Each patient will fill a questionnaire regarding his treatment experience in a VAS scoring from 1-10. The questionnaire will include several questions related to oral hygiene, pain and discomfort experienced throughout the trial.

B] Data management:

A colleague outside the research team will enter the data and organize it in excel sheets in the computer of the orthodontic department.

Data will include all photographs, models, radiographs and filled questionnaire.

C] Statistical Analysis:

- The principle investigator will be responsible for the extraction of the required data from the CBCT taken before and after retraction as well as the study models taken at every follow up visit. The data will be sent to a specialized statistician.

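### T0 in the two-step arm is contradictory: read in the written order, the primary duration leaves out canine retraction in that arm only

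*Combined protocol and SAP*

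**What the plan says.** All references are to the combined protocol and SAP.

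- **Section I) C] Interventions, Clinical Procedure.** For the en-masse arm: "After leveling and aligning is completed (right before retraction), the patient will be referred for the uptake of pre-intervention records for en masse group". For the two-step arm, canine retraction comes first, and "once canine retraction stage is completed, the patient will be referred for the uptake of pre-intervention records".
- **Section I) C], next two blocks.** The acquisition of the pre-intervention records is followed by the block headed "Begin of Retraction". That block describes hooks distal to the lateral incisor and a chain to the molar hooks, which is retraction of the anterior segment. The acquisition block itself places the impressions before retraction and makes no exception by arm.
- **Section I) D] Outcomes.** "All outcomes will be assessed as the difference between T0 at the start of retraction and T1 after complete space closure".
- **Section I) E] Participant timeline.** Item 4, at enrolment: "each participant will be asked for pre-intervention records to ensure proper diagnosis". Item 7 starts the active intervention after levelling and alignment, with no distinction by arm. Item 8: "The principle investigator will take pre-retraction records for every participant T0". Item 9 then lists only anterior segment retraction. Canine retraction is not a step in this timeline.
- **Section III) A] Data collection methods.** The primary outcome is named as "Total Retraction Duration: to assess the timing of antero-posterior movement of anterior teeth and first molars". Anchorage loss is read from CBCT before and after retraction.
- **Outcome measure table.** Sources for duration are digital models, taken monthly, and visit records: "computerized record system of the recruited patient (months, days, years".

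**The concern.** The research question is whether closing the space in one step is faster than closing it in two. The rationale expects two-step to be slower because a canine stage precedes the incisor stage. If the two-step clock starts after the canine stage, the time that the trial exists to compare is removed from one arm and kept in the other.

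Such an omission has a known direction: it shortens the two-step duration and leaves the en-masse duration unchanged. It can hide or reverse a true en-masse advantage, or create a two-step advantage where there is none. Randomisation and blinded assessment of models do not correct it, because it lies in the definition of the outcome.

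The same T0 governs all outcomes. If the two-step baseline model is taken after canine retraction, model-based space closure and anchorage loss during that stage may have no starting point. Prospective pain recording may also begin late in that arm, although the post-retraction questionnaire covers the period in retrospect.

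**Working it through.** **Step 1: the two readings side by side**

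| Text | Where two-step T0 falls |
|---|---|
| I) C] Clinical Procedure: two-step records after canine retraction | After the canine stage |
| I) C]: the block that begins retraction follows those records | After the canine stage |
| I) E] items 8 and 9: pre-retraction records are T0, then anterior segment retraction | After the canine stage, if these are the same records |
| I) D]: T0 is the start of retraction | Before the canine stage, on plain wording |
| I) C] acquisition block: impressions before retraction | Before the canine stage, on plain wording |
| I) E] item 7: active intervention starts after levelling | Before the canine stage |
| III) A]: total retraction duration | Before the canine stage |

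No sentence adds canine time to a duration counted from the later point, so the two readings give different values of the primary outcome for the same patient.

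**Step 2: inputs**

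Section I) F] gives a difference of 1.0, SD 0.76, alpha 0.05, power 0.8, and 10 per group raised to 15 for dropout. Three things are assumed:

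- The test is two-sided, because the null is one of no difference.
- The 1.0 and 0.76 refer to the primary duration. Their unit is not stated.
- The omitted canine time c is the same for every patient, so the SD stays at 0.76. The documents give no value for c, so a range is shown.

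**Step 3: reproduce the plan's figure**

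n per group = 2(1.96 + 0.8416)² × 0.76² / 1.0² = 2 × 7.849 × 0.5776 = 9.07, rounded up to 10. The stated 10 reproduces. With the noncentral t for two independent groups, power is 0.795 at 10 per group and 0.935 at 15. The sample size arithmetic is not the problem here.

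**Step 4: effect of the later T0**

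Measured difference (two-step minus en-masse) = true difference − c.

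Standard error = 0.76 × √(2/n), which is 0.278 at n = 15 and 0.340 at n = 10. The noncentrality parameter is the measured difference divided by the standard error, with 2n − 2 degrees of freedom.

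Example: with a true difference of 1.0, c = 0.5 and n = 15, the measured difference is 0.5, the noncentrality is 0.5 / 0.278 = 1.80, and the chance of a significant result is 0.413.

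True difference 1.0 in favour of en-masse:

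| c omitted | Measured difference | En-masse significantly shorter, n = 15 | Same, n = 10 | Two-step significantly shorter, n = 15 | Same, n = 10 |
|---|---|---|---|---|---|
| 0 | 1.0 | 0.935 | 0.795 | 0.000 | 0.000 |
| 0.25 | 0.75 | 0.742 | 0.551 | 0.000 | 0.000 |
| 0.5 | 0.5 | 0.413 | 0.285 | 0.000 | 0.000 |
| 1.0 | 0 | 0.025 | 0.025 | 0.025 | 0.025 |
| 1.5 | −0.5 | 0.000 | 0.000 | 0.413 | 0.285 |
| 2.0 | −1.0 | 0.000 | 0.000 | 0.935 | 0.795 |

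True difference 0, n = 15: the chance of a false significant advantage for two-step is 0.138 at c = 0.25, 0.413 at c = 0.5 and 0.935 at c = 1.0. The nominal chance in that direction is 0.025.

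A simulation of 40,000 trials per case, for the true difference of 1.0, agreed within 0.6 percentage points.

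**The case against.** The strongest reply is that the Clinical Procedure text never mentions T0 or a duration clock. The bias appears only if its pre-intervention records are taken to be the pre-retraction records of timeline item 8. The labels differ, and item 4 uses the first label for diagnostic records at enrolment. The explicit definition, in Outcomes, is the start of retraction. Canine retraction is retraction, and item 7 starts the active intervention straight after levelling in both arms. The visit records would also hold the date canine retraction began, so the primary duration could be recovered.

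Much of this stands. An investigator who follows Outcomes and item 7 would compute an unbiased duration, and the dates are probably available. It is therefore not established that canine time will be left out. But this is one side of a contradiction, not a resolution of it. The two-step arm has an explicit, arm-specific instruction that puts its baseline after the canine stage, and the next block is the one that begins retraction. Nothing says which rule governs the clock. A visit date can be recovered later, but a baseline model not taken before canine retraction cannot.

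The reply is also right that the power figures are illustrative. Canine-stage length would vary between patients and could change the two-step SD. The source of 0.76 is a cited study that the reference list does not contain. The calculation uses an independent-groups test, in line with the sample size section, whereas the analysis section names a paired t-test. The direction of the bias, and its confinement to one arm, depend on none of these.

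**Conclusion.** The concern holds. The primary outcome has no single start point in the two-step arm, and the reading that follows the written procedure drops canine retraction from that arm alone. This must be fixed before the primary outcome is computed.

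Under that reading, the mean difference shifts against en-masse by exactly the mean length of the omitted stage. An omitted stage longer than the planned difference of 1.0 would reverse the sign of the planned effect. An omission of half that difference would cut power from 0.935 to 0.413 at 15 per group, or from 0.795 to 0.285 at 10. Under the other reading there is no such bias.

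Confidence is high that the passages conflict. How large the bias would be in practice cannot be told from the documents. The probabilities rest on 1.0 and 0.76 being on the duration scale, a constant omitted time and an unchanged SD.

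**What to change.** Reconcile Clinical Procedure, the block that begins retraction, Outcomes and the participant timeline as follows:

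1. Define T0 once for both arms: after levelling and alignment, before any retraction force. In the two-step arm that is before canine retraction.
2. Take the models, photos and pain sheet at that point in both arms. Use one name for these records, distinct from the diagnostic records at enrolment.
3. Define the primary duration in both arms as the time from the first retraction activation, canine or en-masse, to complete space closure, dated from the visit records.
4. Keep the post-canine record set in the two-step arm as an interim time point, and add canine retraction to the timeline.
5. Compute anchorage loss and pain from the common T0, and state when the baseline CBCT is taken relative to it.

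The cost is protocol wording plus at most one added record set (impression, photos, pain sheet) in the two-step arm. Only the timing of measurement changes; treatment does not.

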
Rationale for carrying out the trial:

In order to achieve patient satisfaction and shortest treatment duration, there is no gold standard guidelines which technique achieves the most efficient results at the shortest period of time of retraction. The first premolars are usually the main choice of extraction in bimaxillary protrusion cases, maximum anchorage of the posterior teeth become of great importance for two reasons; first to retract the anterior teeth to their greatest extent and second to increase the chances of correcting the profile maximum retraction of anterior teeth into the extraction space and retraction is the ideal treatment choice. (2,3)

Space closure can be achieved by two methods either the two-steps (4) or by en-masse technique. A debate was raised between the two methods regarding friction mechanics.

It has been recommended that two steps techniques would provide less load on the posterior teeth thus minimal anchorage loss but on the other hand, separate canine retraction followed by incisors retraction would take longer time than closing it in a single step and it is aesthetically unacceptable (5) for some patient as there is a space after canine retraction and it persists up until the full retraction of anterior segment, for these reasons en-masse retraction is expected to be superior treatment option as retraction will be done by one step (6).

Nowadays, Orthodontists prefer using the en-masse technique because of its simplicity and the extraction space will be closed in one step so better aesthetics. But theoretically this technique may provide more loads on posterior segment so more risk of anchorage loss.

In general orthodontic treatment takes long time especially in extraction cases by average two years treatment time (7). So the longer treatment duration, the greater risks on the dentition by a way of root resorption (8), periodontal disease and enamel decalcifications (9). Thus, reduction of the treatment duration is of prime concern to both the patient as well as the orthodontist.

For many years, practitioners have been looking for an efficient force system that can close extraction spaces quickly, aesthetically, accurately, and effectively. It was determined that both were effective methods for retraction (10). However, there is no evidence which technique offers shorter treatment duration with best retraction and space closure.

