Barlow and Kuala 2008 (15) carried out a systematic review concerning the factors that affect the efficiency of closing an extraction space using sliding mechanics. Ten prospective clinical trials that compare the rates of closure under different variables and focus only on sliding mechanics were selected. The results showed that the clinical research was supported by laboratory results, where NiTi coil springs produce a more consistent force and a faster rate of closure when compared with active ligatures as a method of force delivery to

close extraction space. Moreover elastomeric chains was found to produce similar rates of closure compared to Ni-Ti Springs. Finally arch wire size has no effect on the rate of closure, although the larger wire sizes control tipping more effectively.

Kanuru RK *et al.* 2014 (16) carried out clinical study to investigate the amount of space closure by movement of canines into the extraction spaces using four brands of elastomeric power chains (EPCs) by intraoral application with pre-adjusted appliance for 6 weeks, namely the Ormco, 3M Unitek, Rocky Mountain, and Highland, which were closed-link with five loops delivering less than or equal to 250 g were used. The rates of canine retraction were measured between the attachment points on the canine bracket hook and first molar hook using a Mitutoyo Digital Vernier Caliper at the time of first application, after 3 weeks of use, and at the end of 6 weeks of use, and were subjected to statistical calculations. Although all brands of the EPCs produced space closure of canines, it was observed that not much of a significant difference existed among the products tested.

Chaudhari and Tarvade 2015 (17) compared the clinical effectiveness of nickel titanium (NiTi) closed coil spring and elastomeric chain on the rate of space closure, taking into account the anterior retraction and the anchorage loss. Forty patients undergoing orthodontic treatment for bimaxillary proclination were randomly selected after first premolar extraction. They were then allocated to two groups: NiTi closed coil spring group versus Elastomeric chain group, with 20 candidates in each group. The results of the study showed that faster space closure with significant anchorage loss was achieved using NiTi closed coil spring compared to the elastomeric chain.

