Al muzian *et al.* 2017 (18) conducted meta-analysis to explore the effectiveness of nickel titanium closing springs and elastomeric power chains (EPC) in orthodontic space closure and to assess the adverse periodontal effects, cost efficiency and patient-centred outcomes between both of these methods, and they concluded that both of NiTi closing springs and elastomeric chains are efficient force delivery systems in closing extraction space with space closure being the resultant of anterior teeth retraction, anchorage loss or combination.

3) 3D digital model scanning and its reliability

El-Beialy and Mostafa Y.A. 2010 (19) compared the accuracy of dental measurements taken with calipers on 34 orthodontic plaster dental casts to those from computed tomography scans of the same dentition. The mesiodistal widths of teeth, arch widths, arch lengths, arch perimeters, and palatal depths were made with the calipers on a plaster cast. The patients were also scanned with computed tomography, and measurements were made digitally with 3DD, a 3-dimensional-based dental measurements program. The results showed high correlation between the conventional method and the 3DD in all the 3 planes of space. Thus, 3D dental measurement programs (such as the one used in this study) can be a valid alternative to conventional stone dental models.

Kim *et al.* 2016 (20) analysed the accuracy of Bolton analysis obtained from digital models scanned with Ortho Insight (3D) laser scanner system in comparison to those obtained from cone beam computed tomography (CBCT)

images and traditional plaster models. CBCT scans and plaster model's scans were obtained from fifty patients. Bolton ratios were calculated with the Ortho Insight 3D laser scanner software, CBCT scans were imported and analyzed using AVIZO software and plaster models were measured with a digital caliper. Laser scanned digital models were found to be highly accurate compared to physical models and CBCT scans for assessing the spatial relationship of dental arches for orthodontic diagnosis.

Database search:

A search was performed on electronic databases (PubMed, Cochrane library).

Aim of the study

A-PICOS format:

Population:

Adolescent and adult orthodontic patients requiring first premolars extraction.

Intervention:

En-masse retraction using sliding mechanics (friction) with mini screws used as anchorage.

Comparator:

Two-steps retraction using sliding mechanics (friction) with mini screws used as anchorage.

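### Time to space closure answers the treatment-duration question, but the plan also calls it duration of retraction, and no stated analysis separates anterior retraction from forward molar movement

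*Combined protocol and SAP*

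**What the plan says.** The Outcomes section (I, D) defines the endpoint: "Primary outcome: is to monitor the Duration of space closure during en-masse and two steps retraction". It sets the clock in the next sentence: "All outcomes will be assessed as the difference between T0 at the start of retraction and T1 after complete space closure". The participant timeline likewise takes the T1 records after complete space closure.

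Elsewhere the same quantity is described as retraction. The primary objective reads "Evaluating the duration of En-masse and two steps retraction using friction mechanics", the null hypothesis refers to duration of retraction, and Data collection methods (III, A) names the primary outcome total retraction duration. The research question is different again: it asks whether en-masse retraction gives a shorter treatment duration.

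On what closes the space, the Friction Mechanics part of the literature review reports a meta-analysis as describing "space closure being the resultant of anterior teeth retraction, anchorage loss or combination". It also cites a trial in which "faster space closure with significant anchorage loss was achieved using NiTi closed coil spring compared to the elastomeric chain". Of en-masse retraction, the Rationale says: "But theoretically this technique may provide more loads on posterior segment so more risk of anchorage loss".

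Anchorage loss is a secondary outcome. The Statistical Analysis section (III, C) lists a t-test between groups, which it names friction and frictionless, and an ANOVA for the rate of anterior segment retraction. It does not say that the ANOVA compares the arms, and it does not relate duration to anchorage loss.

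**The concern.** Closure and retraction are used as if they were one quantity, but on the protocol's own account they differ by the amount the molars move forward. If one arm loses more anchorage, its space closes sooner even when its anterior teeth move no faster. The trial enrols patients who need maximum anchorage, so the distinction matters to readers.

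A significant difference in duration would then have two explanations: faster retraction, or similar retraction speed with more molar movement and less retraction. The planned analysis does not say how to tell them apart, so the wording of the conclusion would be chosen after the data are seen.

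**Working it through.** **The plan's own figure.** The sample size section gives a difference of 1.0, SD 0.76, power 0.8 and type I error 0.05. No unit is stated. Two-sided, n per group = 2 × (1.960 + 0.842)² × 0.76² / 1.0² = 2 × 7.85 × 0.5776 = 9.07, rounded up to 10. This matches the plan; an exact t calculation gives power 0.795 at 10 per group. The plan then raises 10 to 15 for dropout. None of this is in dispute.

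**Effect of molar movement on the endpoint.** Let S be the space at T0, m the forward molar movement and r the speed of anterior retraction. Then

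closure time = (S − m) / r.

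If S and r are equal in the two arms and one arm has Δm more molar movement, that arm closes sooner by Δm / r. The documents give no retraction rate, so r is assumed, and months are assumed as the unit.

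- Δm = 0.5 mm, r = 0.7 mm/month: 0.5 / 0.7 = 0.71 month.
- Δm = 0.5 mm, r = 1.3 mm/month: 0.5 / 1.3 = 0.38 month.
- Δm = 0: no shift at any r.

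**Chance that such a shift is significant.** The calculation uses a two-sided independent t-test with SD 0.76 and no true difference in retraction speed:

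| Δm (mm) | r (mm/month) | Shift (months) | 10 per group | 15 per group |
|---|---|---|---|---|
| 0.25 | 1.0 | 0.25 | 11% | 14% |
| 0.5 | 1.5 | 0.33 | 15% | 21% |
| 0.5 | 1.0 | 0.50 | 29% | 41% |
| 0.5 | 0.75 | 0.67 | 46% | 64% |
| 0.5 | 0.5 | 1.00 | 79% | 94% |

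**How large an excess is plausible.** The cited study of adult Class I women reports about 4 mm of incisor retraction per 1 mm of molar anchorage loss in both groups, so about one fifth of closure comes from the molar. For an assumed space of 5 to 7 mm, that is 1.0 to 1.4 mm in total. A between-arm excess of 0.5 mm would be 0.5 / 1.4 = 36% to 0.5 / 1.0 = 50% of that total. An excess of 1 mm would be 71% to 100% of it, which is a high-end scenario.

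**A second problem with the clock.** The Outcomes section puts T0 at the start of retraction. The Clinical Procedure text takes the pre-intervention records before retraction in the en-masse arm, but after canine retraction in the two-step arm. If those records define T0, the canine phase is left out of the two-step arm only, and neither duration nor rate is comparable between arms.

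**The case against.** The strongest reply is that the endpoint fits the question. The research question and the Rationale are about treatment duration. If a technique closes space sooner partly through molar movement, that is part of its randomised effect on duration, not bias. This stands, and it is why duration should remain primary. It does not cover the places where the result is named duration of retraction.

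Much is also planned already. Miniscrews are used in both arms. The monthly models track anterior teeth and first molars, and anchorage loss is measured. The ending criteria list canine relation, overjet and facial profile as well as closure. If all were required, closure by molar movement with under-retracted incisors might not end the retraction phase. These safeguards reduce the problem without removing it: the Outcomes section ties T1 to space closure alone, and no analysis brings the two components together.

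A reader might infer that the endpoint is biased towards en-masse retraction. The documents do not support that. The Rationale offers the greater anchorage risk only as theory. The trial with faster closure and more anchorage loss compared springs with elastomeric chain, not retraction methods. The study that supplies the 4:1 ratio found no significant difference in anchorage loss between en-masse and two-step retraction.

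**Conclusion.** The point holds as one of interpretation and pre-specification. The primary outcome is valid for time to space closure. By itself it does not show faster retraction, and the plan states no between-arm analysis that would. The distortion is possible, not demonstrated, and could run in either direction depending on which arm loses more anchorage.

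Its size depends on assumed retraction rates, equal starting space, and reading 1.0 and 0.76 as months. On that basis a 0.5 mm excess accounts for roughly 40% to 70% of the planned difference, and equal anchorage loss accounts for none of it. No change to the sample size follows. The point merits correction before analysis, but not a redesign.

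**What to change.** Keep duration of space closure as the primary outcome and use that name throughout.

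In Statistical Analysis, turn the analysis of anterior retraction rate into an explicit comparison of en-masse with two-step. For each patient, divide anterior displacement from T0 to T1 by the elapsed time, using the planned models or CBCT, and name the reference structure. Report the difference between arms with a 95% confidence interval. Make this the key supportive analysis, shown beside the primary result and the between-arm difference in anchorage loss with its own interval.

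State in advance that the primary result alone supports the conclusion that space closed sooner, and that faster retraction will be claimed only with reference to the rate estimate and its interval. Do not require the observed mean anterior retraction to be no smaller in the en-masse arm. With no margin, that rule would fail about half the time by chance when true retraction is equal.

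Define one T0 for both arms, at the start of any retraction including canine retraction, by reconciling Clinical Procedure with Outcomes. Take the T0 records at that time. The listed ending criteria and the T1 definition must also be reconciled.

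The cost is a few lines of text, one further analysis of records largely planned already, and possibly a more cautious conclusion. The two-step arm's T0 records may need to be taken earlier than Clinical Procedure now says.
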